2.3.1.3 Cardiac and Skeletal Muscle

Based on the nonclinical findings observed with ASP0367, toxicity of the heart and skeletal muscle have been identified as important potential risks, although they have been observed only in rats but not in monkeys.

Baseline cTnI values in patients with PMM are not well established. Since mitochondrial oxidative phosphorylation is the main source of energy in the heart, responsible over 95% of adenosine triphosphate synthesis [Zdończyk et al, 2020], cardiac involvement in mitochondrial diseases is common with an estimated prevalence of more than 20% in adult mitochondrial disease patients [Limongelli et al, 2010]. A single cTnI level at a fixed time point in patients with PMM is insufficient to determine clinical significance, particularly with biological variability (diurnal variation) and bioanalytic (assay variation) variability.

In addition to routine standard monitoring of safety in the proposed study (0367-CL-1201), the sponsor proposes the following screening activities and repeated sequential monitoring to address the cardiac and skeletal muscle toxicity monitoring:

All participants will undergo screening including cardiac biomarkers and ECG prior to enrollment in the study. This study appropriately excludes PMM patients with clinically significant and unstable cardiovascular disease as described in Exclusion Criteria #12 through 14. As such, the investigator will clinically correlate the cTnI level to assess eligibility. Only participants with a cTnI level below upper limit and a mean QT interval using Fridericia's correction (QTcF) of \leq 450 msec for male participants and \leq 480 msec for female participants will be allowed into the study.

Sequential cardiac muscle monitoring will include assessment of serum cardiac enzymes, including cTnI, cTnT, CK-MB and ECGs at protocol-specified intervals. Participants who experience any signs or symptoms potentially reflecting cardiac involvement will undergo ECG, echocardiogram, and have a cTnI drawn for further evaluation prior to continuing study drug. Participants who develop an increase in cardiac enzymes levels (i.e., increased cTnI) will interrupt investigational product (IP) and will undergo more intensive assessments of cardiac function such as ECG and echocardiogram for further evaluation.

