7.2.1 Laboratory Assessments

- See [Section 10.6, Appendix 6: Clinical Laboratory Assessments] for the list of clinical laboratory tests to be performed and refer to schedule of assessments [Table 1] for timing and frequency.
- At follow-up phone call visits, a blood sample for abbreviated biochemistry will be collected at the participant's home by a qualified healthcare provider from the home healthcare vendor. In addition, at week 2, a blood sample for abbreviated biochemistry and hematology will be collected. These samples should be collected at the participant's home. In case the home healthcare visit is not feasible, the visit can be conducted at the study site. The detailed procedures will be described in the lab manual.
- The investigator or subinvestigator must review the laboratory report, document this review and record any clinically significant changes occurring during the study as an AE. The laboratory reports must be filed with the source documents.
- Clinical significance of out-of-range laboratory findings is to be determined and documented by the investigator or subinvestigator who is a qualified physician. Abnormal laboratory findings associated with the underlying disease are not considered clinically significant unless judged by the investigator to be more severe than expected for the participant's condition.

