7.3.6 Adverse Events of Special Interest

The following (S)AEs are considered of special interest:

- Cardiac tissue injury, indicated by cTnI above ULN (see Appendix 10.9 for reference range) or if the cTnT is above ULN (see Appendix 10.9 for reference range) or baseline if the participant's baseline value of cTnT was above ULN
- Cardiac tissue injury with any signs or symptoms reflecting cardiac involvement, inclusive of new onset shortness of breath confirmed by ECG or echocardiogram
- Skeletal muscle injury indicated by CK increase ≥ 5 times the value of the ULN or the individual's baseline value, whichever is higher judged not related to an explainable increase, including excessive movement, fall or disease state
- Suspected abuse of IP. ASP0367 has high-risk of doping potential and was assigned to category D (i.e., high-risk doping potential in sport). Hence, suspected abuse of IP will be analyzed for its muscle function improving characteristics per Astellas Doping Potential Guideline and will be closely followed up via compliance and participants, who will be expected to meet 100% compliance with IP. Compliance will be assessed by counting returned tablets. Deviations from the prescribed dose regimen will be recorded. When IP is administered at the study site, it will be administered under the supervision of study personnel [Section 6.4 Investigational Product Compliance]. Suspected abuse during study will be reported as special situations per [Section 7.3.7 Special Situations].

AEs (serious or nonserious) of special interest are to be collected in the CRF. If the AEs of special interest are classified as serious, they are to be collected via the SAE worksheet and reported within 24 hours as described in [Section 10.3.6 Reporting Procedures for Serious Adverse Events].

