10.3.1.1 Abnormal Laboratory Findings

Any abnormal laboratory test result (e.g., hematology, biochemistry or urinalysis) or other safety assessment (e.g., vital signs, physical examination or ECGs), including those that

worsen from baseline, that is considered to be clinically significant in the medical and scientific judgment of the investigator and not related to underlying disease, is to be reported as an (S)AE.

Any clinically significant abnormal laboratory finding or other abnormal safety assessment, which is associated with the underlying disease, does not require reporting as an (S)AE, unless judged by the investigator to be more severe than expected for the participant's condition.

Repeating an abnormal laboratory test or other safety assessment, in the absence of any of the above criteria, does not constitute an AE. Any abnormal test result that is determined to be an error does not require reporting as an AE.

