- Cardiac tissue injury defined by cTnI above ULN or if the cTnT is above ULN or baseline if the participant's baseline value was above ULN and a TEAE as pre-defined by a MedDRA search strategy for elevated troponin.
- Cardiac tissue injury with any signs or symptoms defined by an echocardiogram or electrocardiogram interpretation is reported as abnormal, clinically significant and a TEAE as pre-defined by a MedDRA search strategy for cardiac complaints.
- Skeletal muscle injury defined by CK increase >= 5 times the value of the ULN or the individual's baseline value, whichever is higher and a TEAE as pre-defined by a MedDRA search strategy for skeletal muscle injury.

AESIs prior to version 9.0 of the protocol did not include elevations in cTnT in the definition of an AESI but instead only included elevations of cTnI. All participants participated in protocol version 7.0 or earlier; therefore participants for whom elevations in cTnT were observed may not have been identified as having experienced an AESIs during study conduct and for this reason may not have had additional ECG and echocardiographic evaluations performed.

The number and percentage of participants who report AESIs will be summarized by analysis group. In addition, any (serious) AEs that are considered abuse of the study drug will also be collected and followed. The number and percentage of AEs of special interest related to abuse, as classified by SOC and PT will be summarized by analysis group.

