6.5.2 Clinical Laboratory Evaluation

Quantitative values including hematology, biochemistry, and urinalysis will be summarized using mean, standard deviation, minimum, maximum and median by analysis group at each analysis visit. Additionally, a within-participant change will be calculated as the post-baseline measurement minus the baseline measurement and summarized in the same way.

Frequency tabulations of qualitative clinical laboratory variables (urinalysis) will be presented for each analysis group at each visit.

Additionally, amylase, lipase and troponin elevations above the ULN and 2xULN will be summarized by analysis group. The denominator for each criterion will be the number of participants who have at least one value after the day of first IP taken to 28 days after the last dose of IP for the double-blind treatment period of the study or moving to the OLE, whichever comes first.

The number and percentage of participants meeting the criteria during the defined period above will be summarized by analysis group.

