6.5.2.1 Liver Safety Assessment

The liver safety assessments will be summarized by the categories below based on the measurements from ALP, ALT, total bilirubin, AST and their combination. These parameters will be based on measurements from a local laboratory. If the baseline value is above ULN then use the baseline value instead of ULN.

- ALT > ULN, > 2xULN, > 3xULN, > 5xULN, > 10xULN, > 20xULN
- AST > ULN, > 2xULN, > 3xULN, > 5xULN, > 10xULN, > 20xULN
- ALT or AST > ULN, > 2xULN, > 3xULN, > 5xULN, > 10xULN, > 20xULN
- ALP > 1.5xULN, 2xULN, 2.5xULN
- Total Bilirubin > 2xULN
- (ALT or AST > 3xULN) and Total Bilirubin > 2xULN
- (ALT or AST > 3xULN) and ALP < 2xULN and Total Bilirubin > 2xULN

The last 2 criteria where 2 or more parameters are evaluated will be with the measurements on the same day or up to 1 day apart.

The denominator for each criterion will be the number of participants who have at least one value after the day of first dose taken to 28 days after the last dose of IP for the 52 weeks or moving to the OLE, whichever comes first. The number and percentage of participants meeting the criteria by 28 days after the last dose of IP for the 52 weeks or moving to the OLE will be summarized by analysis group.

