6.5.2 Clinical Laboratory Evaluation

Quantitative values including hematology, biochemistry, and urinalysis will be summarized using mean, standard deviation, minimum, maximum and median by analysis group at each analysis visit. Additionally, a within-participant change will be calculated as the post-baseline measurement minus the baseline measurement and summarized in the same way. Each laboratory result will be classified as low (L), normal (N), or high (H) at each visit according to the site supplied reference ranges. For the Placebo and ASP0367 groups, baseline values for CK-MM and CK-MB will be defined as the last non-missing observation prior to the first administration of ASP0367.

Frequency tabulations of qualitative clinical laboratory variables (urinalysis) will be presented for each analysis group at each visit.

Additionally, amylase, lipase and troponin elevations above the ULN and 2xULN will be summarized by analysis group. The denominator for each criterion will be the number of participants who have at least one value after the day of first ASP0367 taken to 28 days after the last dose of ASP0367. The number and percentage of participants meeting the criteria by 28 days after the last dose of ASP0367 will be summarized by analysis group.

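### Neither SAP's text counts participants whose CK reaches five times the higher of ULN and baseline without a coded adverse event

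*SAP*

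**What the plan says.** Protocol section 2.3.1.3 states that "toxicity of the heart and skeletal muscle have been identified as important potential risks" and names CK among the markers for monitoring skeletal muscle.

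Protocol section 7.3.6 makes a CK rise of this size an AESI when it is "judged not related to an explainable increase, including excessive movement, fall or disease state". That section presents all its AESIs as adverse events, serious or not.

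Section 6.5.1 of both SAPs keeps the CK threshold, drops the clause about explainable causes, and adds a second condition: "whichever is higher and a TEAE as pre-defined by a MedDRA search strategy for skeletal muscle injury". The wording is the same in the 52-week and 76-week SAPs.

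Section 6.5.2 of both SAPs adds participant counts that need no adverse event: "amylase, lipase and troponin elevations above the ULN and 2xULN will be summarized by analysis group". Section 6.5.2.1 does the same for ALT, AST, ALP and bilirubin, with a rule for raised baselines: "If the baseline value is above ULN then use the baseline value instead of ULN". CK is in neither set.

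The 76-week SAP alone adds, in section 6.5.2, "Each laboratory result will be classified as low (L), normal (N), or high (H) at each visit".

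**The concern.** Whether a high CK becomes a TEAE depends on the investigator. Protocol section 7.2.1 says: "Abnormal laboratory findings associated with the underlying disease are not considered clinically significant unless judged by the investigator to be more severe than expected". Section 10.3.1.1 adds that a disease-related laboratory finding "does not require reporting as an (S)AE, unless judged by the investigator to be more severe than expected". In a myopathy trial, putting a raised CK down to the disease is an easy judgement to make. Exclusion criterion 6 already expects raised CK, since it excludes raised transaminases only where CK is not elevated.

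A participant can therefore cross the plan's own muscle-injury threshold, have no coded event, and not appear in any count of that threshold. Amylase and lipase receive participant counts, while the marker of a named potential risk does not. What is at stake is sensitivity to a muscle signal in small groups.

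**Working it through.** The plan states no figure to reproduce, so the check compares the counting rules and asks whether other outputs could supply the missing count.

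**1. The rules side by side**

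| Analyte | Participant-level threshold count in SAP text | TEAE needed? |
|---|---|---|
| Liver tests (6.5.2.1, both SAPs) | Multiples of ULN, or of baseline if that is raised | No |
| Amylase, lipase, troponin (6.5.2, both SAPs) | Above ULN and above 2 x ULN | No |
| CK (6.5.1, both SAPs) | 5 x the higher of ULN and baseline | Yes |
| CK (6.5.2, 76-week SAP only) | Low/normal/high class; no fivefold cut-off | No |

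Section 6.1 of the 76-week SAP has categorical data summarised by frequency and percentage. Read with the low/normal/high sentence, this gives a CK count above ULN by visit, but not a fivefold count and not one relative to baseline.

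**2. Can by-visit statistics recover the count?** Take two participants with assumed values, in multiples of ULN. The threshold is 5 x max(ULN, baseline).

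- A: baseline 1, value 5. Threshold 5 x max(1, 1) = 5. Crossed. Change 5 - 1 = +4.
- B: baseline 3, value 10. Threshold 5 x max(1, 3) = 15. Not crossed. Change 10 - 3 = +7.

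The visit maximum (10) and the largest change (+7) both belong to B, who did not cross. A, who did, is hidden. A class defined as above ULN marks both as high. The by-visit summaries also keep one observation per window, average same-day values, and, outside the follow-up visit, drop data more than 7 days after the last dose (section 6.8.1 of both SAPs). A peak on an unscheduled repeat can therefore be missing from the visit maximum. The amylase/lipase/troponin table in the 52-week SAP uses a longer window, to 28 days after the last double-blind dose or the move to open-label treatment.

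**3. Can listings recover it?** Yes, by hand: protocol section 9.4.3.2 has laboratory data listed. That gives no tabulated count by group.

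**4. What one participant weighs**

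- Planned arm: 1/22 = 4.5 percentage points.
- Interim sample: 33/3 = 11 per arm, assuming an equal split; 1/11 = 9.1 percentage points.

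These figures show only the weight of one person in a double-blind arm. They do not estimate how many crossings go uncounted, and they do not apply to the 76-week SAP, whose groups are any-dose ASP0367 and placebo-to-ASP0367.

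**The case against.** The strongest reply is that the SAPs follow the protocol. A reader might infer that requiring a TEAE departs from it. It does not: protocol section 7.3.6 defines AESIs as adverse events, so an AESI count that needs an adverse event is consistent. Protocol section 9.4.3.2 promises only descriptive statistics and listings for laboratory data, and the SAPs already go further. This stands. What remains is the absence of a CK-only count.

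Unexplained crossings also have a route into the data. Section 7.3.6 has AESIs recorded in the CRF, and section 8.1 allows the same CK threshold to require stopping treatment. The 52-week SAP counts treatment discontinuations by reason (6.2.1) and TEAEs leading to withdrawal (6.5.1). A fivefold rise over a participant's own baseline may well be judged more severe than expected and be reported. If the protocol is followed, the uncounted group is mainly rises attributed to disease, movement or falls, which the protocol meant to leave out of the AESI. This narrows the gap but does not close it, because the attribution is a judgement and a plain count would allow it to be checked.

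A reader might also infer that such a participant appears in no participant-level count at all. That goes too far. In the 76-week SAP the high class would capture the value against ULN, and in both SAPs the ALT and AST multiples give an indirect view of muscle injury.

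The cardiac AESIs have the same two-part form, so a reader might extend the point to them. The documents do not support an equal concern. Troponin above ULN is already counted without a TEAE, and echocardiograms are event-triggered, so a count of them would largely show who was tested.

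Finally, the DSMB reviews safety laboratory data unblinded, which is oversight but not a reported analysis. The table specifications named in section 6.1 of both SAPs may already contain a CK table. That cannot be ruled out, so the point is limited to the SAP text.

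**Conclusion.** The point holds as a small reporting gap: the text of both SAPs leaves crossings of the CK threshold without a TEAE uncounted at that threshold, although TEAE-free counts are specified for other analytes. It is an improvement to consider, not an error that undermines the safety analysis.

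Its size is unknown, because the documents give no rate of CK crossings without a TEAE. A reader might infer that drug-related muscle injury is being hidden, or that the arms are treated unequally. Neither is shown. In the double-blind part, attribution is made without knowledge of treatment, so the demonstrated effect is a possible loss of sensitivity. The same cannot be said of the open-label part in the 76-week SAP, but no bias is shown there either.

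The conclusion rests on reading the CK rule as 5 times the higher of ULN and baseline, and on the unseen table specifications not already supplying the count.

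**What to change.** In section 6.5.2 of the 52-week SAP, add for each analysis group the number and percentage of participants with any CK at or above 5 times ULN or baseline, whichever is higher, with no TEAE required. Use the window and denominator already set for the amylase, lipase and troponin counts, and show the existing AESI count beside it.

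Add the same row to section 6.5.2 of the 76-week SAP, using that SAP's own baseline and its window to 28 days after the last ASP0367 dose. Label it descriptive only, since there is no concurrent placebo group and open-label data are included.

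The cost is one row per SAP. CK is in both the full and the abbreviated biochemistry panels (protocol section 10.6), so no new data and no protocol change are needed. Both SAPs are dated July 2024; if they are not reopened, the addition can be documented in the CSR, a route section 1 of each SAP provides. If the table specifications already contain this count, a sentence in the SAP is enough.

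The downside is that some counted participants will have disease-related or exertional rises. The AESI count alongside, and in the 52-week SAP the placebo arm, give the context needed to read them.

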6.5.2 Clinical Laboratory Evaluation

Quantitative values including hematology, biochemistry, and urinalysis will be summarized using mean, standard deviation, minimum, maximum and median by analysis group at each analysis visit. Additionally, a within-participant change will be calculated as the post-baseline measurement minus the baseline measurement and summarized in the same way.

Frequency tabulations of qualitative clinical laboratory variables (urinalysis) will be presented for each analysis group at each visit.

Additionally, amylase, lipase and troponin elevations above the ULN and 2xULN will be summarized by analysis group. The denominator for each criterion will be the number of participants who have at least one value after the day of first IP taken to 28 days after the last dose of IP for the double-blind treatment period of the study or moving to the OLE, whichever comes first.

The number and percentage of participants meeting the criteria during the defined period above will be summarized by analysis group.

6.5.2.1 Liver Safety Assessment

The liver safety assessments will be summarized by the categories below based on the measurements from ALP, ALT, total bilirubin, AST and their combination. These parameters will be based on measurements from a local laboratory. If the baseline value is above ULN then use the baseline value instead of ULN.

- ALT > ULN, > 2xULN, > 3xULN, > 5xULN, > 10xULN, > 20xULN
- AST > ULN, > 2xULN, > 3xULN, > 5xULN, > 10xULN, > 20xULN
- ALT or AST > ULN, > 2xULN, > 3xULN, > 5xULN, > 10xULN, > 20xULN
- ALP > 1.5xULN, 2xULN, 2.5xULN
- Total Bilirubin > 2xULN
- (ALT or AST > 3xULN) and Total Bilirubin > 2xULN
- (ALT or AST > 3xULN) and ALP < 2xULN and Total Bilirubin > 2xULN

The last 2 criteria where 2 or more parameters are evaluated will be with the measurements on the same day or up to 1 day apart.

The denominator for each criterion will be the number of participants who have at least one value after the day of first dose taken to 28 days after the last dose of IP for the 52 weeks or moving to the OLE, whichever comes first. The number and percentage of participants meeting the criteria by 28 days after the last dose of IP for the 52 weeks or moving to the OLE will be summarized by analysis group.

